# Transgene / Confidential Amended Version – Márch 20, 2019

Serum chemistry includes BUN, creatinine, creatinine clearance (Cockcroft-Gault formula), sodium, potassium, magnesium, chloride, bicarbonate, calcium, phosphorus, glucose, total bilirubin, ALT, AST, alkaline phosphatase, LDH, total protein, and albumin.

Urinalysis: Blood, bilirubin, glucose, ketones, nitrite, pH, protein, specific gravity, urobilinogen, and leukocyte esterase; microscopic if leukocyte esterase is abnormal: bacteria, casts, crystals, epithelial cells, mucous, RBC and WBC counts

If positive pregnancy test for women of child-bearing potential (WOCBP) an ultrasound will be performed to confirm pregnancy.

Baseline biopsy should be performed if no archival tumor sample is available to establish HCC diagnosis; optional on-trial biopsy scheduled at the discretion of the investigator for translational research purposes can be performed up to Week 8.

Additional Pexa-Vec boosts may be performed in patients based on a case by case discussion between the investigator and Transgene, on the grounds of individual patient benefit. In any case, Pexa-Vec boosts will be performed no sooner than Week 12 and will be combined with a nivolumab infusion.

Beyond 12 months of treatment, the evaluations will be performed every 12 weeks until documented progression or discontinuation of treatment beyond progression. If study treatments are stopped before documented radiological progression, PFS visits will be performed every 6 weeks to continue radiological assessment until documented progression. m The 28-day safety follow-up visit will be organized at least 28 days after the last treatment intake. In case of prior disease progression, this visit will be merged with the end of study visit. In case of treatment discontinuation without disease progression, the 28-day safety follow-up visit will be distinct from the end of study visit that will only occur after disease progression. In this case, patients will undergo in the meantime PFS follow-up visits.

In case the administrations are distributed over 2 consecutive days, patients will undergo another complete physical examination and recording of vital signs prior to Pexa-Vec administration on the second treatment day.

Every 4 weeks starting at W8

# **APPENDIX 2**

# PERFORMANCE STATUS (ECOG) SCALE

- 0. Fully active, able to carry on all pre-disease performance without restriction.
- 1. Restricted in physically strenuous activity but ambulatory and able to carry out work of a light or sedentary nature, e.g. light house work, office work.
- 2. Ambulatory and capable of self care but unable to carry out any work activities. Up and about more than 50% of waking hours.
- 3. Capable of only limited self-care, confined to bed or chair more than 50% of waking hours.
- 4. Completely disabled. Cannot carry out any self-care. Totally confined to bed or chair.

## **APPENDIX 3**

# GUIDANCE TO THE INVESTIGATOR IN CASE OF IMMUNE-RELATED AES

# **Gastrointestinal Toxicity**

Immune-mediated colitis has been associated with the administration of nivolumab. Diarrhea or colitis was reported in 21% of patients in two trials of nivolumab. Immune-mediated colitis occurred in 2.2% of patients in one trial- of these one patient had Grade 2 colitis, and five had Grade 3 colitis. In the other trial, Grade 3 immune-mediated colitis occurred in 0.9% of patients.

Patients should be advised to inform the investigator if any diarrhea occurs, even if it is mild. Range for time to onset of symptoms of colitis has been 1-6 months.

If the event is of significant duration or magnitude or is associated with signs of systemic inflammation or acute phase reactants (e.g. increased CRP or platelet count or bandemia), it is recommended that sigmoidoscopy (or colonoscopy, if appropriate) with colonic biopsy with three to five specimens for standard paraffin block be performed. If possible, one or two biopsy specimens should be snap frozen and stored.

[figure not shown]
Treatment may be restarted following the resolution of colitis. In addition, if the patient is being managed with corticosteroids, treatment should not be restarted until the steroids have been tapered down to a prednisone dose  $\leq 10$  mg/day. Patients who resume treatment should be monitored closely for signs of renewed diarrhea.

Table on next page provides a summary of dose modification guidelines for gastrointestinal toxicities.

# **Dosing Guidelines for Gastrointestinal Toxicity**

# **GI Adverse Event Management Algorithm**

Rule out non-inflammatory causes. If non-inflammatory cause is identified, treat accordingly and continue I-O therapy. Opiates/narcotics may mask symptoms of perforation. Infliximab should not be used in cases of perforation or sepsis.

Patients on IV steroids may be switched to an equivalent dose of oral corticosteroids (e.g. prednisone) at start of tapering or earlier, once sustained clinical improvement is observed. Lower bioavailability of oral corticosteroids should be taken into account when switching to the equivalent dose of oral corticosteroids.

# Hepatotoxicity

Immune-mediated hepatitis has occurred with the administration of nivolumab.

Patients should be monitored for abnormal liver tests prior to and periodically during treatment. While on this study, patients presenting with right upper-quadrant abdominal pain and/or unexplained nausea or vomiting should have LFTs performed immediately and LFTs should be reviewed before administration of the next dose of study drug.

[figure not shown]
If LFTs increase, neoplastic, concurrent medications, viral hepatitis, and toxic etiologies should be considered and addressed, as appropriate. Imaging of the liver, gall bladder, and biliary tree should be performed to rule out neoplastic or other causes for the increased LFTs. Anti-nuclear antibody, perinuclear anti-neutrophil cytoplasmic antibody, anti-liver-kidney microsomal antibodies, and anti-smooth muscle antibody tests should be performed in an autoimmune etiology is considered.

Patients with LFT abnormalities should be managed according to the guidelines in Table below.

# **Dosing Guidelines for Hepatotoxicity**

# Hepatic Adverse Event Management Algorithm

Rule out non-inflammatory causes. If non-inflammatory cause, treat accordingly and continue I-O therapy. Consider imaging for obstruction.

Patients on IV steroids may be switched to an equivalent dost of oral corticosteroids (e.g., prednisone) at start of tapening or earlier, once sustained dinical improvement is observed. Lower bioavailability of oral conticosteroids should be taken into account when switching to the equivalent dost of oral conticosteroids.

\*PO therapy may be delivered rather than electrostage if AST/AIX 5 at URL and TLAST 5 a URL.

\*\*The recommended starting dose for grade 4 hepatitis is 2 mg/kg/day methylpredmisolome IV.

# **Renal Toxicity**

Immune-mediated nephritis or renal dysfunction occurred with nivolumab treatment. Patients should be monitored for elevated serum creatinine prior to and periodically during treatment and clinically monitored for symptoms of decreased volume of urination, hematuria, peripheral edema, loss of appetite.

[figure not shown]
In one trial, there was increased incidence of elevated creatinine in the nivolumab-treated group as compared to chemotherapy (13% v 9%). Grade 2 or 3 immune-mediated nephritis or renal dysfunction occurred in 0.7% (2/268) of patients. In another trial, the incidence of elevated creatinine was 22%, with Grade 2 immune-mediated renal dysfunction occurring in 0.9% (1/117) patients.

Renal toxicity should be managed according to the guidelines in Table below.

# **Dosing Guidelines for Renal Toxicity**

# Renal Adverse Event Management Algorithm

Rule out non-inflammatory causes. If non-inflammatory cause, treat accordingly and continue I-O therapy

Patients on IV steroids may be switched to an equivalent done of eral continuous roles (e.g. predictore) at start of tapering or earlier, once sustained clinical improvement is observed. Lower biodvaliability of eral continuous should be taken into account when switching to the equivalent dose of oral continuous eral continuous eral

# **Endocrine Toxicity**

[figure not shown]
Immune-mediated hypothyroidism and hyperthyroidism has been associated with the administration of nivolumab. In one trial, Grade 1 or 2 hypothyroidism occurred in 8% (21/268) of patients receiving nivolumab. Grade 1 or 2 hyperthyroidism occurred in 3% (8/268) of patients on nivolumab on that trial, and in 1% (1/102) patients receiving chemotherapy. In another trial, hypothyroidism occurred in 4.3% (5/117) of patients. Hyperthyroidism occurred in 1.7% (2/117) of patients. One patient experienced Grade 2 hyperthyroidism.

Patients with unexplained symptoms such as fatigue, headaches, myalgias, impotence, mental status changes, or constipation should be investigated for the presence of thyroid, pituitary, or adrenal endocrinopathies, as well as for hyponatremia or hyperkalemia. An endocrinologist should be consulted if an endocrinopathy is suspected. TSH and free T4 levels should be obtained to determine if thyroid abnormalities are present. TSH, prolactin, and a morning cortisol level will help to differentiate primary adrenal insufficiency from primary pituitary insufficiency.

Hypothyroidism should be managed according to the guidelines in Table below.

# **Dosing Guidelines for Endocrine Toxicity**

# Endocrinopathy Management Algorithm

Patients on IV steroids may be switched to an equivalent dose of oral corticosteroids (e.g. prednisone) at start of tapering or earlier, once sustained clinical improvement is observed. Lower bioavailability of oral corticosteroids should be taken into account when switching to the equivalent dose of oral corticosteroids.

[figure not shown]
# **Pulmonary Toxicity**

Severe pneumonitis or interstitial lung disease, including fatal cases, have occurred with nivolumab treatment. As such, patients must be monitored for signs and symptoms of pneumonitis. Across clinical trial experience in 691 patients with solid tumors, fatal immune mediated pneumonitis occurred in 0.7% (5/691) of patients receiving nivolumab. In one trial 2.2% (6/268) of patients receiving nivolumab developed immune-mediated pneumonitis, one with Grade 3 and vie with Grade 2 cases. In another trial, immune-mediated pneumonitis occurred in 6% (7/117) of patients receiving nivolumab including five Grade 3 and two Grade 2 cases.

Pulmonary toxicity should be managed according to the guidelines in Table below.

# **Dosing Guidelines for Pulmonary Toxicity**

# Pulmonary Adverse Event Management Algorithm

Patients on Wiscomids may be switched to an equivalent dose of oral controsteroids (e.g. predicione) at start of tapering or earlier, once sustained clinical improvement is obtained. Lower biswadability of oral controsteroids should be taken into account when switching to the equivalent dose of oral controsteroids.

[figure not shown]
# Pericardial and Pleural Effusions

Pericardial and pleural involvement with associated effusions is common in patients with NSCLC and have the theoretical potential to be exacerbated by inflammation associated with antitumor immunity following PD-L1 blockade. Patients presenting with dyspnea, chest pain, or unexplained tachycardia should be evaluated for the presence of a pericardial effusion. Patients with preexisting pericardial effusion should be followed closely for pericardial fluid volume measurements and impact on cardiac function. When intervention is required for pericardial or pleural effusions, appropriate workup includes cytology, LDH, glucose, cholesterol, protein concentrations (with pleural effusions), and cell count. For patients with a pericardial effusion causing end-diastolic right ventricular collapse, treatment may be restarted following the placement of a pericardial window, demonstrations of hemodynamic stability, and resolution of right ventricular dysfunction.

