#### 1.5 Potential risks and benefits associated with Pexa-Vec

The risks associated with Pexa-Vec administration, as described in the patient informed consent form (ICF), are related to: 1/ the occurrence of side-effects observed in previous studies, 2/ the potential occurrence of side effects related to the parent vaccine and not observed in previous studies, i.e., infectious vaccinia complications or peri-/myocarditis 3/ the risks related to the intratumoral procedure described below and 4/ risks for third parties, who may enter into contact with the patient treated with Pexa-Vec (See section 1.2.3.2, ICF and IB).

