#### 1.7 Potential risks and benefits associated with Pexa-Vec-nivolumab combination

For suspected nivolumab-related AEs, based on the severity of the event, management with immunosuppressants may be necessary. In general, dose delays and observation are adequate when low-grade AEs are experienced. For moderate- and high-grade AEs, immunosuppression with corticosteroids should be utilized.

Once the AE has begun to resolve, corticosteroids can be tapered over approximately 3 weeks to 6 weeks (depending on the severity of the AE). Subjects with inflammatory events of any organ category expected to require more than 4 weeks of corticosteroid or other immunosuppressive agents to manage the AE should be considered, especially in the setting of the combination with Pexa-Vec treatment that is contra-indicated in patients with immunosuppression. In such an event, consultation with Transgene Medical Monitor should be sought and Pexa-Vec treatment discontinued.

Combination therapy of nivolumab with Pexa-Vec may result in "landmark" events that are the anticipated addition of events of the same type or involving the same organs. Among these "landmark" events, the most likely ones are flu-like symptoms that may occur usually at a moderate intensity with exposure to each of these compounds. Flu-like symptoms (fever, chills, myalgia, and gastrointestinal symptoms) may then be aggravated by the combination. In addition, the risk of myocarditis rarely occurring with the parent vaccinia virus may be increased by the combination with nivolumab.

It is anticipated that a treatment with the combination may also result in hepatic cytolysis (increase in liver enzymes, AST and ALT) and/or in interference with liver function, especially in patients with cirrhosis. AST and ALT elevations, as well as increases in bilirubin, prothrombin time (INR) translated into Child-Pugh score aggravation are deemed "landmark" events. In addition, increase in incidence or severity of immune-related AEs are also deemed "landmark" events. Severity of immune-related AEs is related to the need for steroid treatment. These events are monitored for dose-escalation in the phase I part of the study. Appendix 3 is summarizing the guidance to the Investigator in case of immune-realted AEs including immune-realted hepatic AEs and may be supplemented by discussions with Transgene Medical Monitor.

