#### 5.2 Nivolumab

### 5.2.1 Characteristics, supply, packaging and labelling

Nivolumab is a programmed death receptor-1 (PD-1) blocking antibody marketed by Bristol-Myers Squibb Pharma EEIG. It will be supplied in 40 and/or 100 mg vials (10 mg/mL) in its commercial packaging with brand name "OPDIVO 10 mg/mL concentrate for solution for infusion" (pack size of one 10 mL vial (Type I glass) with a stopper (coated butyl rubber) and a flip-off seal (aluminium), and labelled appropriately as investigational material for this study. Nivolumab concentrate is a clear to opalescent, colourless to pale yellow liquid that may contain few light particles. (See also Summary of Product Characteristics (SmPC).

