## **Discontinuation Criteria**

Treatment should be permanently discontinued for the following (applicable for Phase I and Phase II parts of the study):

- Any Grade 2 drug-related uveitis or eye pain or blurred vision that does not respond to topical therapy and does not improve to Grade 1 severity within the re-treatment period OR requires systemic treatment
- Any Grade 3 non-skin, drug-related adverse event lasting > 7 days, with the following exceptions for drug-related laboratory abnormalities, uveitis, pneumonitis, bronchospasm, hypersensitivity reactions, and infusion reactions, and endocrinopathies:
  - o Grade 3 drug-related uveitis, pneumonitis, bronchospasm, hypersensitivity reaction, or infusion reaction of any duration requires discontinuation
  - o Grade 3 drug-related endocrinopathies adequately controlled with only physiologic hormone replacement do not require discontinuation
  - o Grade 3 drug-related laboratory abnormalities do not require treatment discontinuation except those noted below
- Grade 3 drug-related thrombocytopenia > 7 days or associated with bleeding requires discontinuation
- Any drug-related liver function test (LFT) abnormality that meets the following criteria require discontinuation:
  - o AST or ALT  $> 8 \times ULN$
  - o Total bilirubin > 5 x ULN
  - Concurrent AST or ALT > 3 x ULN and total bilirubin > 2 x ULN
- Any Grade 4 drug-related adverse event or laboratory abnormality, except for the following events which do not require discontinuation:
  - Isolated Grade 4 amylase or lipase abnormalities that are not associated with symptoms or clinical manifestations of pancreatitis and decrease to < Grade 4 within 1 week of onset.
  - Isolated Grade 4 electrolyte imbalances/abnormalities that are not associated with clinical sequelae and are corrected with supplementation/appropriate management within 72 hours of their onset
  - Grade 4 lymphopenia or leucopenia
  - Grade 4 drug-related endocrinopathy adverse events, such as adrenal insufficiency, ACTH deficiency, hyper- or hypothyroidism, or glucose intolerance, which resolve or are adequately controlled with physiologic hormone replacement (corticosteroids, thyroid hormones) or glucose-controlling agents, respectively, may not require discontinuation after discussion with and approval from the Coordinating Investigator [as allowed by protocol].
  - Any dosing interruption lasting > 6 weeks with the following exceptions:

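### Appendix 3's pericardial effusion paragraph, written for lung cancer and PD-L1 blockade, permits a restart in some drug-related cases where the stopping rules require permanent discontinuation

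*Protocol*

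**What the plan says.** The paragraph headed Pericardial and Pleural Effusions stands in Protocol Appendix 3, the investigator guidance on immune-related adverse events. It opens: "Pericardial and pleural involvement with associated effusions is common in patients with NSCLC". It then says that such effusions could in theory be made worse by "inflammation associated with antitumor immunity following PD-L1 blockade", gives follow-up for patients who already have a pericardial effusion, and lists a work-up that includes cytology. On restart it says: "For patients with a pericardial effusion causing end-diastolic right ventricular collapse, treatment may be restarted following the placement of a pericardial window", with haemodynamic stability and recovery of right ventricular function as the two further conditions.

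The trial itself is in hepatocellular carcinoma. Section 5.2.1 states: "Nivolumab is a programmed death receptor-1 (PD-1) blocking antibody marketed by Bristol-Myers Squibb Pharma EEIG". The other product is Pexa-Vec, a replication-competent vaccinia virus. Exclusion criterion 5 in section 4.2 lists pericardial effusions.

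Three parts of the protocol body bear on whether treatment continues after such an event:

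- Section 6.3.4.1 requires nivolumab to be stopped for good after a life-threatening immune-related event.
- The Discontinuation Criteria in section 6.3.4.2, for both phases, require a permanent stop for "Any Grade 4 drug-related adverse event or laboratory abnormality, except for the following events which do not require discontinuation". They require the same for a drug-related, non-skin Grade 3 event that lasts more than 7 days.
- Section 10.9 tells the investigator to contact the sponsor's Medical Monitor about related Grade 3 or 4 events. The next dose may be postponed until resolution within 30 days; otherwise the product concerned is stopped.

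On risk, section 1.5 names "infectious vaccinia complications or peri-/myocarditis" as potential effects of the parent vaccine not seen in previous studies. Section 1.7 adds that "the risk of myocarditis rarely occurring with the parent vaccinia virus may be increased by the combination with nivolumab".

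**The concern.** The effusion paragraph appears to have been carried over from another setting. It presents effusion mainly as a feature of the tumour, in a disease and with a drug target that are not those of this trial, and then gives an unqualified permission to restart. A site that suspects an immune-related effusion is sent from the stopping rules to Appendix 3 and finds there an instruction that can point the opposite way. At stake is whether one patient, after a serious cardiac event that may be caused by study drug, is stopped for good or restarted, and whether two sites would act alike on the same facts.

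**Working it through.** No arithmetic applies and the plan states no figure on this point. The check sets the texts side by side.

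**1. Do the texts address the same patients?** Yes, in part. Appendix 3 covers immune-related events by its title. Section 6.3.4.2 ends by sending the reader to Appendix 3, and section 1.7 presents that appendix as the investigator's guidance. Judging by the readable headings (gastrointestinal, hepatic, renal, endocrine, pulmonary, effusions, skin, nervous system), the effusion paragraph is the only cardiac text in it; the algorithm figures are not available.

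**2. What does each text condition on?**

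| Text | Cause | Grade or duration | Product | Outcome |
|---|---|---|---|---|
| Appendix 3, effusions | not limited | not limited | treatment, unspecified | restart allowed after three conditions |
| 6.3.4.1 | immune-related | life-threatening | nivolumab | permanent stop |
| 6.3.4.2 | drug-related | Grade 4, or Grade 3 non-skin for more than 7 days | treatment, unspecified | permanent stop |
| 10.9 | related to either product | Grade 3 or 4 | Pexa-Vec and/or nivolumab | consult; postpone up to 30 days, otherwise stop |

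The Grade 4 exceptions in 6.3.4.2 cover amylase or lipase, electrolytes, lymphopenia or leucopenia, and endocrinopathy. The Grade 3 special cases name no pericardial or cardiac event either.

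**3. Where do they contradict each other?**

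- Effusion unrelated to study drug, for example malignant: the drug-related criteria do not apply. No contradiction.
- Drug-related, Grade 4: Appendix 3 allows a restart and 6.3.4.2 requires a permanent stop. Contradiction.
- Immune-related and life-threatening: the same contradiction with 6.3.4.1, for nivolumab.
- Drug-related, Grade 3 for more than 7 days: contradiction with 6.3.4.2.
- Drug-related, Grade 3 for 7 days or less: no contradiction with 6.3.4.2; section 10.9 still applies, with a 30-day limit that Appendix 3 does not carry.

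**4. What grade is the event?** The documents do not reproduce the CTCAE grading of pericardial effusion. Section 10.2 matches Grade 4 to life-threatening and explains that as a risk of death when the event occurs. Placing right ventricular collapse that needs a pericardial window in that grade is an inference from this definition.

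**5. Eligibility.** Appendix 3 gives follow-up for a pre-existing pericardial effusion, while exclusion criterion 5 lists pericardial effusions. The criterion opens with clinical significance, so a minor effusion might still be admitted on one reading. The two texts need to be aligned.

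**6. Vaccinia risk.** Sections 1.5 and 1.7 describe a risk and set no restart rule. Appendix 3 is silent on that risk, so this is an omission.

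**The case against.** The best defence is that the texts can be read together. Appendix 3 is guidance and its restart wording is permissive, while section 6.3.4.2 is directive, so the stopping criteria would limit the appendix wherever both apply. The opening on tumour-related effusions and the request for cytology suggest that malignant effusions were mainly in mind, and for those nothing conflicts. Nor is a site left with the appendix alone. Section 10.9 calls for contact with the Medical Monitor on related Grade 3 or 4 events. Section 14.4 convenes the Independent Safety Committee within days of a product-related severe or serious event that may require a decision on study conduct.

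Much of this stands. The conflict is confined to drug- or immune-related events of qualifying grade, and the review steps make an unexamined restart less likely. What does not stand is the claim that the stopping criteria silently prevail. No passage says so, section 6.3.4.2 refers the reader to Appendix 3 without ranking the two, and the restart wording has no carve-out for drug-related events. Section 10.9 adds a third route instead of settling the matter, since it too leaves room to resume after a related Grade 4 event that resolves in time.

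**Conclusion.** The point holds in a conditional form. The paragraph does not fit this trial's disease or drug target, and for drug- or immune-related effusions that are Grade 4 or life-threatening, or Grade 3 beyond 7 days, it contradicts the permanent-stop rules. This rests on the documents as they stand and, for the Grade 4 case, on the inference from section 10.2. The documents give no frequency and the event is expected to be rare, so the size is per event: one patient's continuation decision. No endpoint, sample size, population or analysis changes.

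A reader might infer more, and the documents do not support it:

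- That the paragraph contradicts the peri-/myocarditis risk. It only fails to mention it.
- That it authorises renewed exposure to the virus. The product is undefined, the surrounding appendix text is about nivolumab, scheduled Pexa-Vec ends on Day 29, and boosts come no sooner than Week 12 after case-by-case discussion with the sponsor.
- That it alters the Phase I toxicity count. Section 6.2 classifies a dose-limiting toxicity from the event itself, and a later restart does not change that.
- That it weakens cardiac monitoring or reporting. The ECG, echocardiography and troponin schedule in section 8.1, and the immediate reporting of Grade 3 or higher cardiotoxicity in section 10.5, apply regardless.

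**What to change.** The sponsor and the Independent Safety Committee should reconcile the effusion paragraph with sections 6.3.4.1, 6.3.4.2 and 10.9 and with exclusion criterion 5, and state which passage governs. The paragraph should then be reworded for hepatocellular carcinoma and this combination, so that it:

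- refers to the governing rule instead of setting a separate one;
- says which effusions the restart wording covers, drug-related or not;
- says to which product or products it applies;
- agrees with the eligibility criterion on pre-existing effusion;
- points to the peri-/myocarditis risk in sections 1.5 and 1.7.

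Which clinical rule is right is for the sponsor and the committee; none is proposed here. The cost is one paragraph of Appendix 3 at the next amendment, with a matching cross-reference in section 6.3.4.2 if wanted. No visit, procedure or analysis is added.
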